8.1.10 Premature discontinuation of trial product

If a subject prematurely discontinues trial product, the investigator must aim to undertake procedures similar to those for the end of treatment (V25) as soon as possible, and a follow-up visit (V26) two weeks later.

The subjects must be asked to attend additional visits depending on when the trial product discontinuation takes place during the trial:

- If the trial product is discontinued before V19 subjects must be asked to attend three additional visits (V19x, V25x and V30x) taking place weeks 30, 56 and 82 after randomisation, respectively.
- If the trial product is discontinued after V19 and before V25 subjects must be asked to attend two additional visits (V25x and V30x) taking place weeks 56 and 82 after randomisation, respectively.

The primary reason for premature discontinuation of trial product must be specified on the end of trial form in the eCRF, and final drug accountability must be performed. A treatment discontinuation session must be made in the IWRS.

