8.4.13 Hypoglycaemic episodes

At randomisation, all subjects must be instructed in symptom recognition and handling of hypoglycaemia.

Plasma glucose should always be measured and recorded when a hypoglycaemic episode is suspected.

All plasma glucose values:

- \leq 3.9 mmol/L (70 mg/dL) or
- $>$ 3.9 mmol/L (70 mg/dL) occurring in conjunction with hypoglycaemic symptoms

should be reported in the diary according to the instructions below throughout the trial from randomisation to V25. See Section [8.6.3.2](#).

Upon onset of a hypoglycaemic episode the subject is recommended to measure plasma glucose every 15 minutes until the SMPG value is $>$ 3.9 mmol/L (70 mg/dL) and/or symptoms have been resolved in accordance to current guidelines⁴⁸.

A SMPG value \leq 3.9 mmol/L (70 mg/dL) or hypoglycaemic symptoms must trigger a hypoglycaemic episode form to be completed by the subject. Repeated SMPG measurements and/or symptoms, occurring within a period of 60 min after onset on a hypoglycaemic episode, will by default be considered as one hypoglycaemic episode until a succeeding SMPG value is $>$ 3.9 mmol/L (70 mg/dL) and/or symptoms have been resolved and should be reported on one hypoglycaemic episode form. SMPG measurements \leq 3.9 mmol/L (70 mg/dL) or hypoglycaemic symptoms after the 60 min period shall trigger the reporting of a new hypoglycaemia episode and prompt the subject to fill out a new hypoglycaemic episode form until a succeeding measurement is $>$ 3.9 mmol/L (70 mg/dL) and/or symptoms have been resolved.

In case of several low SMPG values within the 60 minutes interval, the lowest value is the one that will be reported as the SMPG value for the hypoglycaemic episode but the start time of the episode will remain as the time for the first SMPG value and/or symptom.

The record should include the following information:

- Start date and time of the hypoglycaemic episode.
- The plasma glucose level before treating the episode (if available) and any follow up measurements.
The lowest value measured during the hypoglycaemic episode will be reported as the plasma glucose value for the episode. The remaining values will be kept as source data in the diary.
- Whether the episode was symptomatic (Yes/No).
A hypoglycaemic episode starting without symptoms should be updated to symptomatic if the subject experience symptoms later during the episode.

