12.1 Definitions

12.1.1 Adverse event

An adverse event (AE) is any untoward medical occurrence in a subject administered a medicinal product, and which does not necessarily have a causal relationship with this treatment.

An AE can therefore be any unfavourable and unintended sign (including an abnormal laboratory finding), symptom or disease temporally associated with the use of a product, whether or not considered related to the product.

An AE includes:

- A clinically significant worsening of a concomitant illness.
- A clinical laboratory adverse event (CLAE): a clinical laboratory abnormality which is clinically significant, i.e. an abnormality that suggests a disease and/or organ toxicity and is of a severity that requires active management. Active management includes active treatment or further investigations, for example change of medicine dose or more frequent follow-up due to the abnormality.

The following should **not** be reported as AEs:

- Pre-existing conditions, including those found as a result of screening or other trial procedures performed before exposure to trial product (pre-existing conditions should be reported as medical history or concomitant illness).
- Pre-planned procedures unless the condition for which the procedure was planned has worsened from the first trial-related activity after the subject has signed the informed consent.
- Non-serious hypoglycaemia is an AE, but is reported on a hypoglycaemic episode form instead of on an AE form; see Section [8.4.13](#).

The following three definitions are used when assessing an AE:

- **Severity**
 - **Mild** – no or transient symptoms, no interference with the subject's daily activities.
 - **Moderate** – marked symptoms, moderate interference with the subject's daily activities.
 - **Severe** – considerable interference with the subject's daily activities; unacceptable.
- **Causality**

Relationship between an AE and the relevant trial products:

 - **Probable** - Good reason and sufficient documentation to assume a causal relationship.
 - **Possible** - A causal relationship is conceivable and cannot be dismissed.
 - **Unlikely** - The event is most likely related to aetiology other than the trial product.

- **Final outcome**

- **Recovered/resolved** - The subject has fully recovered, or by medical or surgical treatment the condition has returned to the level observed at the first trial-related activity after the subject signed the informed consent.

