12.2 Reporting of adverse events

All events meeting the definition of an AE must be collected and reported. This includes events from the first trial-related activity after the subject has signed the informed consent until the end of the post-treatment follow-up period (week 82). The events must be recorded in the applicable eCRF forms in a timely manner; see timelines below and [Figure 12-1](#).

During each contact with the trial site staff, the subject must be asked about AEs and technical complaints, for example by asking: “Have you experienced any problems since the last contact?”

All AEs, either observed by the investigator or subject, must be reported by the investigator and evaluated.

All AEs must be recorded by the investigator on an AE form. The investigator should report the diagnosis, if available. If no diagnosis is available, the investigator should record each sign and symptom as individual AEs using separate AE forms.

For SAEs, a safety information form must be completed in addition to the AE form. If several symptoms or diagnoses occur as part of the same clinical picture, one safety information form can be used to describe all the SAEs.

For all non-serious AEs, the applicable forms should be signed when the event is resolved or at the end of the trial at the latest.

Timelines for initial reporting of AEs:

[figure not shown]
The investigator must complete the following forms in the eCRF within the specified timelines:

SAEs: The AE form **within 24 hours** and the safety information form **within 5 calendar** days of the investigator's first knowledge of the SAE. Both forms must be signed within 7 calendar days from the date the information was entered in the eCRF.

For SAEs requiring reporting on a specific event form: In addition to the above the specific event form within **14 calendar days** from the investigator's first knowledge of the AE.

If the eCRF is unavailable, the concerned AE information must be reported on a paper AE form and sent to Novo Nordisk by fax, e-mail or courier within the same timelines as stated above. When the eCRF becomes available again, the investigator must enter the information on the form into the eCRF. See Section [13](#).

Contact details (fax, telephone, e-mail and address) are provided in the investigator trial master file.

Timelines are for the completion of forms from the time of investigator's awareness

AEs requiring specific event forms are described in Section 12.1.4 and 12.1.5

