17.4.1.2 Safety endpoints

Adverse events

AEs will be summarised for the safety analysis set separately for three periods:

- Run-in period: defined as events with onset date between V2 (included) and the first day of trial product administration (not included).
- In-trial period: defined as events with onset date between the first day of trial product administration and the last study visit.
- On-treatment period: defined as events with onset date between the first day of trial product administration and whatever comes first: a) 14 days after the last day on trial product , b) follow-up visit (V26 for subjects with trial product discontinued), or c) last study visit (subjects withdrawn without follow-up visit).

A treatment-emergent adverse event (TEAE) is defined as an event that occurs in the “on-treatment” period.

The AEs will be coded using the most recent version of the Medical Dictionary for Regulatory Activities (MedDRA). They will be presented in terms of the number and percentage of subjects with at least one event, the number of events and the event rate per 1000 years. AEs in the screening period (prior to randomisation) will be presented in listings.

Hypoglycaemic episodes

Hypoglycaemic episodes will be summarised descriptively by severity and treatment in terms of the number and percentage of subjects with at least one episode and the total number of episodes. Separate summaries will be made by severity (the ISPAD criterion for severe hypoglycaemia⁴⁹). In

the same way as for AEs, there will be separate summaries for the “in-trial” and “on-treatment” periods. Hypoglycaemic episodes in the screening period will be presented in listings.

Classification of Hypoglycaemia

Treatment emergent: hypoglycaemic episodes will be defined as treatment emergent if the onset of the episode occurs on or after the first day of trial product administration, and no later than 14 days after the last day on trial product.

Nocturnal hypoglycaemic episodes: are episodes occurring between 23:00 and 07:00 both inclusive.

[figure not shown]
Hypoglycaemic episodes are classified according to ISPAD’s definition of severe hypoglycaemia⁴⁹ as well as the Novo Nordisk classification of hypoglycaemia; see [Figure 17–1](#) and the ADA classification of hypoglycaemia; see [Figure 17–2](#)).

Novo Nordisk classification of hypoglycaemia in paediatrics

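### Diary reporting of hypoglycaemia stops at V25, but the protocol's treatment-emergent and in-trial summaries and its AE collection rule run past it, and neither document reconciles them

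*Protocol*

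**What the plan says.** **Collection.** Protocol 8.4.13 asks for plasma glucose values at or below 3.9 mmol/L, and higher values with symptoms. These "should be reported in the diary according to the instructions below throughout the trial from randomisation to V25". V25 is the week 56 end-of-treatment visit.

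**Analysis.** In Protocol 17.4.1.2 an episode is treatment-emergent if it starts on or after the first dose "and no later than 14 days after the last day on trial product". The same section says "there will be separate summaries for the “in-trial” and “on-treatment” periods", as for adverse events, and defines the in-trial period as ending at the last study visit. The measures are the number and percentage of subjects with an episode and the number of episodes.

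**General AE rule.** Protocol 12.1.1 states: "Non-serious hypoglycaemia is an AE, but is reported on a hypoglycaemic episode form instead of on an AE form". Protocol 12.2 requires all adverse events to be collected to week 82, with subjects asked about them at each contact.

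**Early discontinuation.** Under Protocol 8.1.10, when trial product is stopped early, "the investigator must aim to undertake procedures similar to those for the end of treatment (V25) as soon as possible". A V26 follows two weeks later, and a separate V25x is held at week 56.

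**SAP.** Section 2.4.1.2 keeps treatment-emergent hypoglycaemic episodes as a safety endpoint. Section 3.3, which lists changes to the safety analyses, does not mention hypoglycaemia.

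**The concern.** The number of treatment-emergent hypoglycaemic episodes is a listed safety endpoint (Protocol 4.2.2.2). Its analysis window is wider than the stated window of the diary that feeds it, and the in-trial summary is wider still.

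A site that follows 8.4.13 stops diary reporting at V25. A site that follows 12.2 carries on. Capture after V25 can therefore differ between sites for reasons unrelated to treatment. A reader of the in-trial table could also take it to rest on the same quality of reporting throughout, when its last 26 weeks may not.

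**Working it through.** **1. Timeline.** SAP Table 3-1 gives V25 = day 393, V26 = day 407 and V30 = day 575. With scheduled day = 7 × week + 1:
- week 56: 7 × 56 + 1 = 393
- week 58: 7 × 58 + 1 = 407
- week 82: 7 × 82 + 1 = 575

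All three agree with the table.

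**2. Completer, last dose on day 393.** Share outside the diary window = days of the analysis window after V25 ÷ all days of that window.
- Treatment-emergent: 14 ÷ (393 + 14) = 14 ÷ 407 = 3.4%
- In-trial: (575 − 393) ÷ 575 = 182 ÷ 575 = 31.7%

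If V25 is assumed to move by 4 days either way, the first share runs from 14 ÷ 411 = 3.4% to 14 ÷ 403 = 3.5%. The second runs from 178 ÷ 575 = 31.0% to 186 ÷ 575 = 32.3%.

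**3. Early discontinuer.** Section 8.4.13 does not say which visit V25 denotes once treatment has stopped early.

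*If it is the visit held at discontinuation*, all 14 post-dose days lie outside the diary window. The documents give no stop times, so those below are assumptions, with last dose on day 7 × week + 1:

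| Assumed stop | Last dose | Share of treatment-emergent window outside diary |
|---|---|---|
| Week 8 | day 57 | 14 ÷ 71 = 19.7% |
| Week 20 | day 141 | 14 ÷ 155 = 9.0% |
| Week 30 | day 211 | 14 ÷ 225 = 6.2% |
| Week 45 | day 316 | 14 ÷ 330 = 4.2% |

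*If it is week 56*, there is no gap for anyone whose last dose is on or before day 393 − 14 = 379.

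The visit labels do not settle the matter. Protocol 8.1.10 calls the week 56 visit of a discontinuer V25x, and SAP 3.4.1 uses V25 for the visit held at discontinuation. That makes the first reading available, but 8.4.13 does not adopt it.

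**4. What can still be recorded after V25.**
- Episodes meeting SAE criteria also go on an AE form and a safety information form (8.4.13).
- Subjects are asked about adverse events at each contact to week 82 (12.2).
- The subject demonstrates a glucose measurement at each visit (8.4.2), and the diary description in 8.6.3.2 gives no stop visit.

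**5. What these routes do not replace.**
- An open question about problems since the last contact cannot find an episode without symptoms, yet both classifications in 17.4.1.2 have an asymptomatic category.
- One reading per visit, kept in the medical record, is not surveillance between visits.
- After V26 the visits are at weeks 64, 70, 76 and 82, six weeks apart. Section 8.4.13 itself treats non-severe episodes not written up within 7 days as less valid data.

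**The case against.** The strongest reply is that the V25 limit sits in one sentence about the diary, and that the rest of the protocol keeps collection open. Section 12.2 runs to week 82. Section 12.1.1 moves non-serious hypoglycaemia to its own form and does not drop it. The sentence in 8.4.13 that triggers an episode form names no end visit. The flowchart rows for the meter and diaries are broken in the available text and might settle the matter in the original.

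This stands against a stronger conclusion that a reader might draw: that nothing is asked after V25 and that the post-dose window is empty by rule. The documents do not support that. They conflict on collection after V25; they do not exclude it.

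Several points on size also stand:
- The listed endpoint is treatment-emergent episodes, where a completer's gap is 3.4%. The 31.7% belongs to a supplementary summary.
- No exposure-adjusted rate is stated for hypoglycaemia, so no person-time denominator is diluted.
- The diary rule is the same in both blinded arms, and SAP 2.4.1.2 plans no formal safety tests unless otherwise stated.
- For a subject withdrawn without a follow-up visit, the on-treatment period ends at the last study visit, so that summary contains no full 14-day tail.
- Section 8.4.2 asks for measurements between visits only when an episode is suspected, so asymptomatic capture is limited before V25 too.

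One might also infer from the 40% withdrawal assumed in Protocol 17.1 that the larger early-stopper shares are common. That does not follow: the 40% is cumulative to week 56 and says nothing about timing.

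Finally, Protocol 5.5 gives a half-life of about 13 hours, so five half-lives (5 × 13 = 65 hours) end early in the 14-day tail. That could justify a narrower analysis window. It does not justify leaving the window wider than collection.

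**Conclusion.** The inconsistency is real. The stated diary window is shorter than both analysis windows and than the general AE collection period, and neither document explains or resolves this.

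For a completer, 3.4% of treatment-emergent days and 31.7% of in-trial days lie after it, assuming last dose at V25 and visits on schedule. For early discontinuers the treatment-emergent gap is either the full 14 days or, for anyone stopping at least 14 days before week 56, nil. Which applies depends on a reading that the protocol leaves open.

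What is lost or left to site practice is systematic capture of non-serious, mainly asymptomatic, episodes after V25. That an in-trial table would be read as 82 weeks of uniform reporting is an inference about readers, not something that the plan states. The weight is minor to moderate, and the primary endpoint is unaffected.

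**What to change.** Reconcile 8.4.13 with 12.1.1, 12.2 and 17.4.1.2:

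1. In 8.4.13, extend diary and episode-form reporting to V26 for every subject, including the V26 held two weeks after premature discontinuation. A completer's uncovered treatment-emergent days then fall from 14 of 407 to 0. This also removes the ambiguity about V25 for discontinuers.
2. For the in-trial summary, choose one of two routes. Either continue the same reporting to V30/V30x, which takes the uncovered in-trial days from 182 of 575 to 0. Or drop the in-trial hypoglycaemia summary, or restrict it to the collected period with a footnote giving that period.
3. Record the choice in the SAP, and check that the flowchart rows for the glucose meter and diaries match it.

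The cost is a change of wording and about two more weeks of a diary and meter that subjects already have, or 26 weeks if reporting runs to V30. No new device or visit is needed. If collection can no longer be changed, restricting the summaries and adding the footnote still resolves the mismatch on the reporting side.

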- Was the hypoglycaemic episode associated with severe neuroglycopenia, usually resulting in coma or seizure and requiring parenteral therapy (glucagon or intravenous glucose)?⁴⁹ (Layman language used in the diaries: Was the low blood glucose episode associated with symptoms severe enough to result in unconsciousness or a seizure and was glucagon (an injection) or IV glucose/sugar (drip) needed for your child to recover?).
If the severity of a hypoglycaemic episode aggravates, only one hypoglycaemic episode should be reported reflecting the most severe degree of hypoglycaemia.
- Date, time and dose of last trial product administration prior to the episode
- Date and time of last main meal (not including snacks) prior to the episode
- Whether the episode occurred in relation to physical activity
- Change in any concomitant illness.
- Any sign of fever and/or other acute disease.
- Whether the subject was asleep when the episode occurred
 - If yes, whether the symptoms of the episode woke up the subject

If the question "Was the hypoglycaemic episode associated with severe neuroglycopenia, usually resulting in coma or seizure and requiring parenteral therapy (glucagon or intravenous glucose)?" is answered "YES", the hypoglycaemic episode is classified as "severe"⁴⁹ and the following information should be recorded:

- Who assisted in the treatment of the hypoglycaemic episode (i.e. medical person or non-medical person)?
- Where the treatment was administered (in clinic/emergency room/hospital or other. If the subject was treated in clinic/emergency room/hospital, whether they were transported in an ambulance or not)
- Type of treatment provided by other person (i.e. oral carbohydrates, glucagon, IV glucose or other)
- Were symptoms alleviated after administration of treatment?

- Factors contributing to the episode (i.e. physical activity, missed meal, diet change, medication error (i.e. overdose, mix-up between products, incorrect use of device), other factors not listed or unknown).
- Did the subject experience seizure?
- Did the subject experience loss of consciousness?
- Did the subject experience any of the following symptoms⁴⁹ (layman term used in the diary is specified in brackets if different from the protocol term)?
 - Autonomic: Shakiness, sweatiness, trembling, palpitations (Rapid and irregular heart beat and pallor (extreme paleness))

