 - Neuroglycopenic: Poor concentration, blurred or double vision, disturbed colour vision, difficulty hearing, slurred speech, poor judgment and confusion, problems with short-term memory, dizziness and unsteady gait
 - Behavioural signs and symptoms: Irritability, erratic behaviour, agitation (restlessness associated with irritability and tension), nightmares, inconsolable crying
 - Non-specific symptoms: Hunger, headache, nausea, tiredness
 - Other symptoms?

Oral carbohydrates should not be given if the subject is unconscious.

If the subject experiences a severe hypoglycaemic episode, the subject or LAR should be instructed to contact the investigator as soon as possible after recovery for further guidance.

The investigator must review the diary for low SMPG values not reported as hypoglycaemic episodes. The subject must be questioned whether any of the low values were severe, i.e. whether the subject was able to self-treat or not. If the subject was not able to self-treat, it has to be reported as a severe hypoglycaemic episode.

Low SMPG values for non-severe hypoglycaemic episodes not having a hypoglycaemic episode form completed within 7 days since the SMPG measurement should be reported on a hypoglycaemic episode form with as much information as possible. Novo Nordisk will not query for additional data except for the start date, SMPG value and whether the subject was able to self-treat due to decreased validity of such data^{50, 51}.

The subject must be re-trained in how to report hypoglycaemic episodes if the investigator identifies low SMPG values not reported as hypoglycaemic episodes.

If the hypoglycaemic episode fulfils the criteria for an SAE then an AE form and a safety information form must also be filled in; see Section [12](#).

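### Protocol 8.4.13 has two tests for severe hypoglycaemia, and neither document says which one sets the severe flag for episodes found at diary review

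*Protocol*

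**What the plan says.** **Episode form (Protocol 8.4.13).** The record for each episode includes one severity question: "Was the hypoglycaemic episode associated with severe neuroglycopenia, usually resulting in coma or seizure and requiring parenteral therapy (glucagon or intravenous glucose". A yes classifies the episode as severe and opens further items, including whether there was a seizure or loss of consciousness. The lay version in the diary asks about "symptoms severe enough to result in unconsciousness or a seizure and was glucagon (an injection) or IV glucose/sugar (drip) needed for your child" to recover.

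**Investigator's diary review (also 8.4.13).** The investigator looks for low self-measured plasma glucose (SMPG) values that were not reported as episodes. For these, "The subject must be questioned whether any of the low values were severe, i.e. whether the subject was able to self-treat or not". The rule that follows is: "If the subject was not able to self-treat, it has to be reported as a severe hypoglycaemic episode".

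**Analysis (Protocol 17.4.1.2).** Episodes are summarised descriptively. "Separate summaries will be made by severity (the ISPAD criterion for severe hypoglycaemia"). The written definitions of both the Novo Nordisk and the ADA/ISPAD classifications take the ISPAD question as their severe category.

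**SAP.** Section 2.4.1.2 lists treatment-emergent hypoglycaemic episodes under both classifications. Section 3.3, which records changes to the safety analyses, has no entry on hypoglycaemia.

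**The concern.** The same word is given two meanings within one protocol section, and only one of them is the meaning used in the analysis. Whether an assisted episode is called severe can therefore depend on how it came to light: through a form completed by the subject, or through a value noticed later by the investigator.

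What is at stake is the meaning of the severe row in the hypoglycaemia tables of a paediatric trial. Someone reading an ISPAD-severe count will take it that every episode in it involved severe neuroglycopenia with parenteral therapy. If reports made under the review rule enter that row unchanged, this is no longer assured. If they are removed at the programming stage instead, that is done without a prespecified rule.

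**Working it through.** The protocol gives no expected rate or count of severe hypoglycaemia, so there is no figure to reproduce. The check is to apply each rule to the same episode.

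**Step 1: the three rules side by side.** Take a low SMPG value found at diary review with no episode form.

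| What happened | Form question (8.4.13) | Diary-review rule (8.4.13) | Analysis criterion (17.4.1.2) |
|---|---|---|---|
| Subject treated the episode unaided | Not severe | Not severe | Not severe |
| Another person gave oral carbohydrates; no coma, seizure or parenteral therapy | Not severe | **Severe** | Not severe |
| Unconsciousness or seizure, with glucagon or intravenous glucose needed | Severe | Severe | Severe |

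The rules part in the second row only.

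**Step 2: direction.** A subject who is unconscious or having a seizure and needs parenteral therapy was not, in practice, able to self-treat. The ISPAD set therefore lies inside the set defined by inability to self-treat. Carrying review-rule reports into the severe category can add episodes to it but not remove any.

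**Step 3: can a site comply with both?** The route to severe stated for the form is a yes to the ISPAD question. For the second-row episode the truthful answer is no, yet the review rule requires it to be reported as severe. The site must either answer the form question wrongly or disregard the review rule. Ability to self-treat is not among the record items listed in 8.4.13, so the protocol names no separate place to put that information.

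**Step 4: where a carried-over flag would show.** Under ADA/ISPAD, a second-row episode with a value at or below 3.9 mmol/L would move from the documented symptomatic or asymptomatic category into severe. Under the Novo Nordisk classification it depends on the value. Below 3.1 mmol/L the episode is already BG-confirmed, so the combined severe-or-BG-confirmed category is unchanged and only the severe row grows. From 3.1 to 3.9 mmol/L the episode is not BG-confirmed, so the severe flag alone would bring it into the combined categories as well.

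**Step 5: is there a reconciling rule?** I found none in Protocol 8.4.13 or 17.4.1.2, or in SAP 2.4.1.2 or 3.3. Figures 17–1 and 17–2 are not visible in the text available, so this rests on the written category definitions.

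**The case against.** The best reply is that every analysis passage uses one criterion. If the programs classify on the ISPAD question alone, an assisted-only episode never reaches the severe row, whatever the site was told to report. This largely stands. A reader might infer that the severe counts *do* mix two definitions, but the documents do not establish it. Mixing follows only if the as-reported flag is carried into the tables, and that is left open. What remains is that the site instruction and the analysis criterion disagree and nothing says how the disagreement is resolved.

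A reader might also infer that the ISPAD class of late-found episodes is lost, because "Novo Nordisk will not query for additional data except for the start date, SMPG value and whether the subject was able to self-treat". That is a misreading. The limit is set for non-severe episodes with no form completed within 7 days, so it does not cover an episode just reported as severe. Even those late non-severe forms are to be filled in as fully as possible. For severe episodes the record includes "Type of treatment provided by other person (i.e. oral carbohydrates, glucagon, IV glucose or other"), along with seizure and loss of consciousness, which together would largely show whether ISPAD was met. These items are formally opened by a yes to the ISPAD question, so their completion for an assisted-only episode is uncertain. Uncertain is not the same as unrecoverable.

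It is also fair to say that the affected set is narrow: a low value in the diary, no episode form, help from another person, and no ISPAD-level event. The endpoint is supportive and the same rule applies in both blinded arms.

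**Conclusion.** The inconsistency is real and visible on the face of the protocol. Section 8.4.13 requires some episodes to be reported as severe that its own form question and the analysis in 17.4.1.2 would not call severe, and neither document names the governing field.

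The scope is limited to low SMPG values found at the investigator's diary review; forms completed by subjects use the ISPAD question. Protocol 4.2.2.2 lists the endpoint as supportive secondary safety, it is summarised descriptively, and SAP 2.4.1.2 plans no formal safety analyses unless otherwise stated. The primary analysis, the sample size and the type I error rate are untouched.

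The size cannot be calculated. With few events even one extra episode could be noticeable, but any percentage would come entirely from an assumed number of true severe events, for which the documents offer no basis. The conclusion that tables would include non-ISPAD episodes is conditional on the as-reported flag being used. The direction, upward only, assumes that an ISPAD-severe episode is never self-treated.

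**What to change.** Reconcile the form question, the diary-review rule and the analysis criterion so that one definition sets the severe flag. Which definition is for the sponsor to decide; this point does not favour either. Then:

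- ask the form's severity question at diary review too, so that an episode is classified the same way however it is found;
- record ability to self-treat as its own item rather than as a synonym for severe;
- collect treatment type, seizure and loss of consciousness for every assisted episode, not only after a yes to the ISPAD question;
- state in the SAP which data field determines severe in both classifications, and how an episode is handled if the site's report and that field disagree.

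The cost is small: one revised review question, one eCRF field with a changed trigger for the follow-up items, a note to sites, and a sentence or two in the SAP before database lock. If data have already been collected, the SAP statement can still be made, with a listing of episodes reported as severe without a yes to the ISPAD question.
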